2.4.9 Onset Status of Adverse Drug Reactions or Infections by Sex Group

Statistical Analysis Set	Safety-evaluable patients in this special drug use surveillance
Details of Statistical Analysis	Classify the patient population into males and females, and compile ADR types. The compilation method of ADR types is the same as described in section 2.4.1.
Figure/Table No.	Table 2.4.9

2.4.10 Onset Status of Adverse Drug Reactions or Infections by Age Group

Statistical Analysis Set	Safety-evaluable patients in this special drug use surveillance
Details of Statistical Analysis	Classify the patient population into 64 years or below, 65 to 74 years, and 75 years or over, and compile ADR types. The compilation method of ADR types is the same as described in section 2.4.1.
Figure/Table No.	Table 2.4.10

2.4.11 Onset Status of Adverse Drug Reactions or Infections by BMI

Statistical Analysis Set	Safety-evaluable patients in this special drug use surveillance
Details of Statistical Analysis	Classify the patient population into less than 18.5 kg/m ² , 18.5 to less than 25 kg/m ² , 25 to less than 30 kg/m ² , 30 kg/m ² or over, and compile ADR types. The compilation method of ADR types is the same as described in section 2.4.1.
Figure/Table No.	Table 2.4.11

2.4.12 Onset Status of Adverse Drug Reactions or Infections by Complications

Statistical Analysis Set	Safety-evaluable patients in this special drug use surveillance
Details of Statistical Analysis	Compile ADR types by presence or absence of complications. The compilation method of ADR types is the same as described in section 2.4.1.
Figure/Table No.	Table 2.4.12

2.4.13 Onset Status of Adverse Drug Reactions or Infections by Presence or Absence of Hypertension

Complications

Statistical Analysis Set	Safety-evaluable patients in this special drug use surveillance
Details of Statistical Analysis	Compile ADR types by presence or absence of hypertension complications. The compilation method of ADR types is the same as described in section 2.4.1.
Figure/Table No.	Table 2.4.13

2.4.14 Onset Status of Adverse Drug Reactions or Infections by Presence or Absence of Diabetes

Complications

Statistical Analysis Set	Safety-evaluable patients in this special drug use surveillance
Details of Statistical Analysis	Compile ADR types by presence or absence of diabetes complications. The compilation method of ADR types is the same as described in section 2.4.1.
Figure/Table No.	Table 2.4.14

2.4.15 Onset Status of Adverse Drug Reactions or Infections by Presence or Absence of Liver

Complications

Statistical Analysis Set	Safety-evaluable patients in this special drug use surveillance
Details of Statistical Analysis	Compile ADR types by presence or absence of liver complications. The compilation method of ADR types is the same as described in section 2.4.1.
Figure/Table No.	Table 2.4.15

2.4.16 Onset Status of Adverse Drug Reactions or Infections by Presence or Absence of Kidney

Complications

Statistical Analysis Set	Safety-evaluable patients in this special drug use surveillance
Details of Statistical Analysis	Compile ADR types by presence or absence of kidney complications. The compilation method of ADR types is the same as described in section 2.4.1.
Figure/Table No.	Table 2.4.16

2.4.17 Onset Status of Adverse Drug Reactions or Infections by Presence or Absence of Cardiac

Complications

Statistical Analysis Set	Safety-evaluable patients in this special drug use surveillance
Details of Statistical Analysis	Compile ADR types by presence or absence of cardiac complications. The compilation method of ADR types is the same as described in section 2.4.1.
Figure/Table No.	Table 2.4.17

2.4.18 Onset Status of Adverse Drug Reactions or Infections by Presence or Absence of Cerebrovascular Complications

Statistical Analysis Set	Safety-evaluable patients in this special drug use surveillance
Details of Statistical Analysis	Compile ADR types by presence or absence of cerebrovascular complications. The compilation method of ADR types is the same as described in section 2.4.1.
Figure/Table No.	Table 2.4.18

2.4.19 Onset Status of Adverse Drug Reactions or Infections by Presence or Absence of Bleeding-related Event Complications

Statistical Analysis Set	Safety-evaluable patients in this special drug use surveillance
Details of Statistical Analysis	Compile ADR types by presence or absence of bleeding-related event complications. The compilation method of ADR types is the same as described in section 2.4.1.
Figure/Table No.	Table 2.4.19

2.4.20 Onset Status of Adverse Drug Reactions or Infections by Presence or Absence of Concomitant Anticoagulant and/or Antiplatelet Drugs

Statistical Analysis Set	Safety-evaluable patients in this special drug use surveillance
Details of Statistical Analysis	Compile ADR types by presence or absence of concomitant anticoagulant or antiplatelet drugs (Concomitant anticoagulant / antiplatelet , Anticoagulant only, Antiplatelet only, Neither). The compilation method of ADR types is the same as described in section 2.4.1.
Figure/Table No.	Table 2.4.20

2.4.21 Onset Status of Adverse Drug Reactions (Bleeding-Related Events) by Presence or Absence of Concomitant Anticoagulant and/or Antiplatelet Drugs

Statistical Analysis Set	Safety-evaluable patients in this special drug use surveillance
Details of Statistical Analysis	Compile the types of adverse drug reactions (bleeding-related events) by presence or absence of concomitant anticoagulant or antiplatelet drugs (Concomitant anticoagulant / antiplatelet , Anticoagulant only, Antiplatelet only, Neither). The compilation method of the types of adverse drug reactions is the same as described in section 2.4.1.
Figure/Table No.	Table 2.4.21

2.4.22 Onset Status of Adverse Drug Reactions or Infections by Baseline Fasting Triglyceride Level

Statistical Analysis Set	Safety-evaluable patients in this special drug use surveillance whose fasting triglyceride levels were measured at baseline
Details of Statistical Analysis	Compile ADR types by baseline fasting triglyceride level (Less than 150 mg/dL, 150 to less than 400 mg/dL, 400 to less than 500 mg/dL, 500 to less than 750 mg/dL, 750 mg/dL or over). The compilation method of ADR types is the same as described in section 2.4.1.
Figure/Table No.	Table 2.4.22

2.4.23 Onset Status of Adverse Drug Reactions or Infections by Baseline Random Triglyceride Level

Statistical Analysis Set	Safety-evaluable patients in this special drug use surveillance whose random triglyceride levels were measured at baseline
Details of Statistical Analysis	Compile ADR types by baseline random triglyceride level (Less than 150 mg/dL, 150 to less than 400 mg/dL, 400 to less than 500 mg/dL, 500 to less than 750 mg/dL, 750 mg/dL or over). The compilation method of ADR types is the same as described in section 2.4.1.
Figure/Table No.	Table 2.4.23

2.4.24 Onset Status of Adverse Drug Reactions or Infections by Initial Dose

Statistical Analysis Set	Safety-evaluable patients in this special drug use surveillance
Details of Statistical Analysis	Compile ADR types by initial dose. The compilation method of ADR types is the same as described in section 2.4.1.
Figure/Table No.	Table 2.4.24

2.4.25 Onset Status of Adverse Drug Reactions or Infections by Breakdown of Change in Daily Dose

Statistical Analysis Set	Safety-evaluable patients in this special drug use surveillance
Details of Statistical Analysis	Compile ADR types by breakdown of change in daily dose (2 g → 4 g, 4 g → 2 g, Other). The compilation method of ADR types is the same as described in section 2.4.1.
Figure/Table No.	Table 2.4.25

2.4.26 Onset Status of Adverse Drug Reactions or Infections by Presence or Absence of Concomitant

Antihyperlipidemic Drug Use (during observation period)

Statistical Analysis Set	Safety-evaluable patients in this special drug use surveillance
Details of Statistical Analysis	Compile ADR types by presence or absence of concomitant antihyperlipidemic drug use. The compilation method of ADR types is the same as described in section 2.4.1.
Figure/Table No.	Table 2.4.26

2.4.27 Onset Status of Adverse Drug Reactions or Infections by Presence or Absence of Concomitant

Statins Drugs

Statistical Analysis Set	Safety-evaluable patients in this special drug use surveillance
Details of Statistical Analysis	Compile ADR types by presence or absence of concomitant statins drugs. The compilation method of ADR types is the same as described in section 2.4.1.
Figure/Table No.	Table 2.4.27

2.4.28 Onset Status of Adverse Drug Reactions or Infections by Presence or Absence of Concomitant

Fibrate Drugs

Statistical Analysis Set	Safety-evaluable patients in this special drug use surveillance
Details of Statistical Analysis	Compile ADR types by presence or absence of concomitant fibrate drugs. The compilation method of ADR types is the same as described in section 2.4.1.
Figure/Table No.	Table 2.4.28

2.4.29 Onset Status of Adverse Drug Reactions or Infections by Presence or Absence of Concomitant

Intestinal Transporter Inhibitors

Statistical Analysis Set	Safety-evaluable patients in this special drug use surveillance
Details of Statistical Analysis	Compile ADR types by presence or absence of concomitant intestinal transporter inhibitors. The compilation method of ADR types is the same as described in section 2.4.1.
Figure/Table No.	Table 2.4.29

2.4.30 Onset Status of Adverse Drug Reactions or Infections by Presence or Absence of Concomitant

Anion-exchange Resin

Statistical Analysis Set	Safety-evaluable patients in this special drug use surveillance
Details of Statistical Analysis	Compile ADR types by presence or absence of concomitant anion-exchange resin. The compilation method of ADR types is the same as described in section 2.4.1.
Figure/Table No.	Table 2.4.30

2.4.31 Onset Status of Adverse Drug Reactions or Infections by Presence or Absence of Concomitant

Nicotinic Acid Derivatives

Statistical Analysis Set	Safety-evaluable patients in this special drug use surveillance
Details of Statistical Analysis	Compile ADR types by presence or absence of concomitant nicotinic acid derivatives. The compilation method of ADR types is the same as described in section 2.4.1.
Figure/Table No.	Table 2.4.31

2.4.32 Onset Status of Adverse Drug Reactions or Infections by Presence or Absence of Concomitant

Probucol

Statistical Analysis Set	Safety-evaluable patients in this special drug use surveillance
Details of Statistical Analysis	Compile ADR types by presence or absence of concomitant probucol. The compilation method of ADR types is the same as described in section 2.4.1.
Figure/Table No.	Table 2.4.32

2.4.33 Onset Status of Adverse Drug Reactions or Infections by Presence or Absence of Concomitant

Ethyl Icosapentate (EPA)

Statistical Analysis Set	Safety-evaluable patients in this special drug use surveillance
Details of Statistical Analysis	Compile ADR types by presence or absence of concomitant ethyl icosapentate (EPA). The compilation method of ADR types is the same as described in section 2.4.1.
Figure/Table No.	Table 2.4.33

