5.0 Dosage and Administration for Study Population

The usual adult dosage is 2 g of omega-3 fatty acid ethyl esters administered orally once daily after meals. However, the dosage can be increased up to twice daily (at a dose of 2 g) depending on the patient's triglyceride level.

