9.3 Treatment Information

1) Survey items

Administration of the Drug (daily dose, treatment duration, and status of completion of treatment with the Drug), administration of antihyperlipidemic drugs other than the Drug* (presence or absence, drug name, daily dose, and treatment duration), and administration of concomitant medications (other than antihyperlipidemic drugs) (presence or absence, drug name, and purpose of administration)

*: Including antihyperlipidemic drugs with which treatment is discontinued within two months before baseline.

2) Survey timing

Period from baseline to Month 12 (or discontinuation of treatment)

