9.6 Adverse Events (AEs)

1) Survey items

Presence or absence of AE (see Table 1), AE name, date of onset, seriousness and reason for seriousness (see Table 2), action taken to the Drug, date of determination of outcome, outcome, and causal relationship to the Drug* (see Table 3)

If the outcome is not resolved or unknown and the causal relationship is determined as unevaluable, follow-up survey should be conducted to some extent possible.

*If causal relationship to the Drug is determined as not related, reasons that may constitute the rationale for determination should be collected if it is unevaluable.

2) Survey timing

Period from baseline to Month 12 (or discontinuation of treatment)

3) Priority survey item

Bleeding-related events occurring after baseline are set as a priority survey item. If any bleeding-related event is reported as an AE, laboratory test values related to bleeding should be separately collected.

Table 1 Definition of Adverse Event

An adverse event (AE) is any untoward medical occurrence in a patient administered a medicinal product and which does not necessarily have to have a causal relationship with this treatment.
 
An AE can therefore be any unfavorable and unintended sign (including an abnormal laboratory finding, for example), symptom, or disease temporally associated with the use of a medicinal product, whether or not considered related to the medicinal product.
 
The following should be also handled as an AE:
 
• A symptom or other problem occurring in an infant breastfed from a mother taking the medicinal product• A symptom or other problem occurring in a child administered the medicinal product• A symptom or other problem occurring in a patient administered or taking more than the approved dose of the medicinal product
--

Table 2 Seriousness Criteria

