Details of Statistical Analysis	
Compile the following items for the prior-approval status and per survey unit period of the special drug use surveillance.
 
Statistical analysis of ‘number of study sites,’ ‘number of surveyed patients,’ ‘number of patients with ADRs,’ and ‘number of ADRs’ should cover safety-evaluable patients locked during each survey unit period.
 
  
 Item Name	Details of Statistical Analysis	
   
 Number of study sites	Number of medical institutions that have collected eCRFs	
 
 Number of surveyed patients	Number of safety-evaluable patients.	
 
 Number of patients with ADRs	Number of patients in which ADRs occurred.	
 
 Number of ADRs	Number of ADRs that occurred. Every PT occurring should be counted as one event.	
 
 Rate of patients with ADRs	Calculated by the following equation: $[\text{Number of Patients with ADRs}] / [\text{Number of Safety-Evaluable Patients}] \times 100$	
 
 ADR type	 
The calculation method in performing each analysis should be as follows:
 
[Number of patients with ADRs]
 
 Number of patients in which ADRs occurred. 
[Number of ADRs]
 
 Number of ADRs that occurred. If the same ADR occurs more than once in the same patient, a total of frequencies of the ADR should be counted. 
[Rate of patients with ADRs]
 
 Calculated by the following equation: $[\text{Number of Patients with ADRs}] / [\text{Number of Safety-Evaluable Patients}] \times 100$. 
[ADR type]
 
 ADRs should be replaced by MedDRA terms. Categorize by SOC and compile ADRs by PT in each category. If SOC is ‘Investigations,’ classify by HLG (sort by HLG code in ascending order but without outputting) and compile ADRs by PT. 
 At SOC level, the numbers and rates of patients with ADRs should be presented by SOC internationally agreed order. If the same SOC occurs more than once in the same patient, ADRs should be counted as one patient in the SOC. At PT level, the numbers and rates of patients with ADRs should be presented by PT code in 	
  
	Item Name	Details of Statistical Analysis	Number of study sites	Number of medical institutions that have collected eCRFs	Number of surveyed patients	Number of safety-evaluable patients.	Number of patients with ADRs	Number of patients in which ADRs occurred.	Number of ADRs	Number of ADRs that occurred. Every PT occurring should be counted as one event.	Rate of patients with ADRs	Calculated by the following equation: $[\text{Number of Patients with ADRs}] / [\text{Number of Safety-Evaluable Patients}] \times 100$	ADR type	
The calculation method in performing each analysis should be as follows:
 
[Number of patients with ADRs]
 
 Number of patients in which ADRs occurred. 
[Number of ADRs]
 
 Number of ADRs that occurred. If the same ADR occurs more than once in the same patient, a total of frequencies of the ADR should be counted. 
[Rate of patients with ADRs]
 
 Calculated by the following equation: $[\text{Number of Patients with ADRs}] / [\text{Number of Safety-Evaluable Patients}] \times 100$. 
[ADR type]
 
 ADRs should be replaced by MedDRA terms. Categorize by SOC and compile ADRs by PT in each category. If SOC is ‘Investigations,’ classify by HLG (sort by HLG code in ascending order but without outputting) and compile ADRs by PT. 
 At SOC level, the numbers and rates of patients with ADRs should be presented by SOC internationally agreed order. If the same SOC occurs more than once in the same patient, ADRs should be counted as one patient in the SOC. At PT level, the numbers and rates of patients with ADRs should be presented by PT code in

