Item Name	Details of Statistical Analysis														
Number of study sites	Number of medical institutions that have collected eCRFs														
Number of surveyed patients	Number of safety-evaluable patients.														
Number of patients with ADRs	Number of patients in which ADRs occurred.														
Number of ADRs	Number of ADRs that occurred. Every PT occurring should be counted as one event.														
Rate of patients with ADRs	Calculated by the following equation: $[\text{Number of Patients with ADRs}] / [\text{Number of Safety-Evaluable Patients}] \times 100$														
ADR type	
The calculation method in performing each analysis should be as follows:
 
[Number of patients with ADRs]
 
 Number of patients in which ADRs occurred. 
[Number of ADRs]
 
 Number of ADRs that occurred. If the same ADR occurs more than once in the same patient, a total of frequencies of the ADR should be counted. 
[Rate of patients with ADRs]
 
 Calculated by the following equation: $[\text{Number of Patients with ADRs}] / [\text{Number of Safety-Evaluable Patients}] \times 100$. 
[ADR type]
 
 ADRs should be replaced by MedDRA terms. Categorize by SOC and compile ADRs by PT in each category. If SOC is ‘Investigations,’ classify by HLG (sort by HLG code in ascending order but without outputting) and compile ADRs by PT. 
 At SOC level, the numbers and rates of patients with ADRs should be presented by SOC internationally agreed order. If the same SOC occurs more than once in the same patient, ADRs should be counted as one patient in the SOC. At PT level, the numbers and rates of patients with ADRs should be presented by PT code in 														

		ascending order. If the same PT occurs more than once in the same patient, ADRs should be counted as one patient in the PT.
	Cumulative total for special drug use surveillance	A respective total of the numbers of study sites and patients per survey unit period. Do not double-count the same medical institution when counting the number of study sites.
Figure/Table No.	Table 2.4.1	

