Details of Statistical Analysis	
Categorize adverse drug reactions (bleeding-related events) by the following categories for each item, and count the types of adverse drug reactions (bleeding-related events). The categories and the compilation method of adverse drug reactions are the same as described in section 2.4.5.

Figure/Table No.	Table 2.4.7

2.4.8 Rate of Patients of Adverse Drug Reactions or Infections by Patient Demographics and Treatment

Details

Statistical Analysis Set	Safety-evaluable patients in this special drug use surveillance	
Details of Statistical Analysis	Categorize ADRs by the following categories for each item and compile the rate of patients with ADRs.	
	Item Name	Category
	Sex	Male, Female
	Age	Minimum age to 64 years, 65 to 74 years, 75 years to maximum age, Unknown
	BMI	Less than 18.5 kg/m ² , 18.5 to less than 25 kg/m ² , 25 to less than 30 kg/m ² , 30 kg/m ² or over, unknown
	Complications	No, Yes
	Complication breakdown	Hypertension, Diabetic, Liver disorder, Kidney disorder, Cardiac disorders Cerebrovascular diseases, Bleeding-related event, Others
	Fasting triglyceride at baseline (mg/dL)	Less than 150 mg/dL, 150 to less than 400 mg/dL, 400 to less than 500 mg/dL, 500mg/dL or over, Not measured
		Less than 150 mg/dL, 150 to less than 400mg/dL, 400 to less than 500 mg/dL, 500 to less than 750 mg/dL, 750 mg/dL or over, Not measured
	Random triglyceride at baseline (mg/dL)	Less than 150 mg/dL, 150 to less than 400 mg/dL, 400 to less than 500 mg/dL, 500mg/dL or over, Not measured
		Less than 150 mg/dL, 150 to less than 400mg/dL, 400 to less than 500 mg/dL, 500 to less than 750 mg/dL, 750 mg/dL or over, Not measured
	Initial dose	2 g, 4 g, other
	Breakdown of presence of change in daily dose	2 g → 4 g, 4 g → 2 g, Other
	Presence or absence of concomitant antihyperlipidemic drug use (during observation period)	No, Yes

	Breakdown of concomitant antihyperlipidemic drugs (during observation period)	statins drugs, fibrate drugs, intestinal transporter inhibitors, anion-exchange resin, nicotinic acid derivatives, probucol, ethyl icosapentate (EPA), others
	Presence or absence of concomitant anticoagulant/antiplatelet drug use (during observation period)	No, Yes
	Breakdown of concomitant anticoagulant/antiplatelet drugs (during observation period)	Anticoagulant drugs, antiplatelet drugs
Figure/Table No.	Table 2.4.8	

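### SAP 2.4.25 and the dose-change row of 2.4.8 class patients by a dose path that an ADR can itself cause, so the '4 g to 2 g' ADR rate can rise with no dose effect

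*SAP*

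**What the plan says.** SAP 2.4.25 is to "Compile ADR types by breakdown of change in daily dose" in three classes: 2 g to 4 g, 4 g to 2 g, and Other. There is no class for patients whose dose did not change. The counting method is that of SAP 2.4.1, which takes the "Number of patients in which ADRs occurred" and, within a preferred term, adds: "If the same PT occurs more than once in the same patient, ADRs should be counted as one patient in the PT". Nothing in that method relates ADR onset to the date of a dose change.

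SAP 2.4.8 has a row labelled "Breakdown of presence of change in daily dose" with the same three classes and compiles the rate of patients with ADRs, again with no timing condition. SAP 1.1 measures onset time from the first administration only. SAP 2.4.24 separately tabulates ADRs by initial dose.

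Protocol 10.4.2, on factors likely to affect safety, names administration of the Drug as a stratification variable for ADR incidence. Protocol 9.3 collects daily dose and treatment duration. For adverse events, Protocol 9.6 collects "Presence or absence of AE (see Table 1), AE name, date of onset" and also "action taken to the Drug, date of determination of outcome".

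**The concern.** Initial dose is fixed before any ADR can occur. A dose path is not: it is known only later, and the event being counted can determine it. A patient who has an ADR on 4 g and is reduced for that reason enters the '4 g to 2 g' row because of the ADR and then counts as an ADR patient in it. A patient without an ADR has no such route into the row.

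Under the protocol's heading of factors likely to affect safety, a reader will compare this row with something. Neither output shows an unchanged group, so the natural comparators are the overall rate in Table 2.4.1 and the '2 g to 4 g' row. A high rate could then be read as a dose pattern when it reflects doses being changed in response to ADRs.

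**Working it through.** **Inputs.** The only overall ADR rate in the documents is in Protocol 1.0: 91/948 = 0.09599, which reproduces the stated 9.6%. Using r = 0.096 as a 12-month risk, equal on both doses, is an assumption. The documents give no frequency of reductions, no share of them due to ADRs, and no share starting on 4 g; these are assumed below. In a stratified row, the denominator is taken to be the safety-evaluable patients in that row.

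**General formula, no dose effect.** Among 4 g starters, let a be the probability of being classed '4 g to 2 g' for patients with an ADR, and b the same probability for patients without one. Then

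row rate = r·a / [r·a + (1 − r)·b].

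If a = b, this equals r. It exceeds r only if a > b.

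**Linking a to ADR-driven reductions.** Let background reductions affect a share b of patients, spread evenly over the year, and let a share p of ADR patients not yet reduced be reduced at onset. With a constant hazard λ = −ln(0.904) = 0.100926, the mean onset as a fraction of the year, given an ADR, is m = 1/λ − 0.904/0.096 = 9.9083 − 9.4167 = 0.492. Among ADR patients:

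- reduced before onset: b·m
- reduced because of the ADR: (1 − b·m)·p
- reduced later for other reasons: b·(1 − m)·(1 − p)

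The sum is a = b + p − b·p, so m affects the ordering but not the row rate. For b = 0.10 and p = 0.10, a = 0.19 and the row rate is 0.096 × 0.19 / (0.096 × 0.19 + 0.904 × 0.10) = 0.01824/0.10864 = 16.8%.

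**Results for b = 0.10.** Onset before the change is the second plus third components, divided by a. Reduced because of the ADR is the second component, divided by a.

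| p | a | Row rate | Row's ADR patients with onset before the change | Row's ADR patients reduced because of the ADR |
|---|---|---|---|---|
| 0 | 0.100 | 9.6% | 51% | 0% |
| 0.05 | 0.145 | 13.3% | 66% | 33% |
| 0.10 | 0.190 | 16.8% | 74% | 50% |
| 0.20 | 0.280 | 22.9% | 82% | 68% |
| 0.30 | 0.370 | 28.2% | 87% | 77% |

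A simulation of 4 million patients under these assumptions agrees with the row rates within 0.1 percentage point.

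**Dependence on b, with p = 0.10.** For b = 0.05, a = 0.145 and the rate is 0.01392/(0.01392 + 0.0452) = 23.5%. For b = 0.20, a = 0.28 and the rate is 0.02688/(0.02688 + 0.1808) = 12.9%.

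**The p = 0 line.** Half of the row's ADR patients had onset before the change, yet the row shows exactly 9.6%. The distortion comes from ADR-driven entry into the row.

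**Cell sizes.** If 5%, 10% or 20% of the 3,000 target patients start on 4 g (150, 300 or 600), the 16.8% case puts a share of 0.10864 in the row: about 16, 33 or 65 patients, of whom about 3, 5 or 11 have an ADR.

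**The case against.** The other side has substance. Both outputs do what Protocol 10.4.2 asks: they compile ADRs in the observation period by administration of the Drug. The row is labelled as a path, and nothing presents it as exposure to 2 g. The current SAP makes no dose comparison from it, and the reader has to fetch a comparator from elsewhere. No passage says that doses are reduced because of ADRs. Protocol 5.0 describes only an increase from the usual 2 g once daily, and patients who stop because of an adverse event, a reason listed in SAP 2.3, do not enter the row through that event. With the cell sizes above, exact 95% intervals for 3/16, 5/33 and 11/65 are 4–46%, 5–32% and 9–28%; all include 9.6%.

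These points limit the size and the severity. They do not remove the mechanism: the SAP itself provides a '4 g to 2 g' class, and its counting rule lets an ADR both place a patient in that class and raise the class's rate.

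Four stronger readings are tempting, and the documents do not support them:

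- **Counting ADRs that began on 4 g is the fault.** The p = 0 line shows no distortion from that alone.
- **A false test result may follow.** Fisher's exact and Mann-Whitney tests for 2.4.8 appear only in superseded SAP versions.
- **The '2 g to 4 g' row is biased in a known direction.** That direction cannot be determined from the documents.
- **A stratified patient-day analysis by dose is needed.** It would be out of proportion for sparse descriptive tables in a plan that uses no patient-time rate.

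**Conclusion.** The point holds as a conditional one, for consideration. If patients with an ADR are more likely to be reduced from 4 g than patients without one, the '4 g to 2 g' rate in SAP 2.4.25 and 2.4.8 exceeds the overall rate with no dose effect. If reductions are unrelated to ADRs, there is no distortion.

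The real size is unknown. The 13.3% to 28.2% range rests on an assumed 10% of background reductions, the 9.6% pre-approval risk applied to 12 months on either dose, and assumed ADR-driven reductions of 5% to 30%. It describes 4 g starters only; the SAP does not say where a patient going from 2 g to 4 g and back is placed. Table 2.4.24 is unaffected. The harm is a rate that may mislead.

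**What to change.** Keep the existing patient counts and Table 2.4.24. In 2.4.25 and the dose-change row of 2.4.8, add:

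- (a) the number of ADR patients whose first ADR began on or before the first dose change, and the number whose first ADR began after it;
- (b) the number of patients whose ADR has a dose change recorded under action taken to the Drug, if that field has such a category (Protocol 9.6 names the field but does not list its options).

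Item (b) is the more direct indicator. In the illustration, (a) already stands at 51% on or before the change when no reduction is due to an ADR.

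Add a footnote saying that patients are classed by dose path; that ADRs may precede or cause the change; that the split shows ordering and is not a rate on each dose; that the rows are not a dose comparison; and that imputed onset dates may misorder events within a month. The last point arises because SAP 1.1 replaces an unknown onset date with the first of the month, or with the start date if the months coincide. The ordering caveat matters because time after the change is shorter than 12 months: at p = 0, the share of the row with onset after the change is only 9.6% × 0.492 = 4.7%, with no dose effect.

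The cost is some programming and no new data collection, since dose history, onset date and action taken are already collected. The downside is sparse cells.
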